10.1 Return of Withdrawn/Removed Subjects

A participant who has withdrawn may not return to the study.

11 Remuneration Plan for Subjects

Participants will not be renumerated for receiving HCV treatment.

Participants will receive \$25 remuneration as gift cards at those visits where stored sample blood draws are completed. Those visits are Screening, week 24, and week 72. If additional visits are needed to obtain bloodwork or imaging, this additional visit would also warrant a \$25 remuneration. We will not exceed a maximum of 3 additional visits and will encourage combined visits.

Participants will receive \$100 remuneration as gift cards provided by UMB study staff whilst working as special volunteers at the NIH site when participants have an MRI. These visits are at the time of day -7 (interim visit) and week 72. [name], [name], [name], and [name], are UMB sub investigators who are also special volunteers at NIH and are fully credentialed and able to see research patients at the NIH. They are also authorized to obtain informed consent, provide remuneration to subjects visiting the NIH site, have access to identifiable data, see patients at NIH and participate in manuscript preparation/review.

12 Monitoring

As this is an observational study with intervention limited to laboratory and radiologic data collection, safety issues are not expected. The PI and the study team will conduct regular monitoring of safety and report to the IRB as specified in section 9.

13 Statistical Considerations

13.1 Sample Size Justification and Power

The proposal primary outcome for cardiovascular risk is change in hsCRP. The primary hypothesis is that HCV eradication will result in at least a two-fold decrease from the baseline elevated hsCRP to 12 months post-functional cure in HCV-monoinfected and HIV/HCV-coinfected patients, respectively. Based on a previous study, mean hsCRP before starting IFN-therapy in HCV-monoinfected patients was 0.97 ± 0.11 mg/L compared to 0.07 ± 0.07 mg/L in healthy controls(23). Among SVR patients the median hsCRP at baseline was 0.64 mg/L and decreased to 0.25 mg/L after treatment. With a sample size of 30 patients in each group, we assume than 95% will achieve SVR with Zepatier (elbasvir/grazoprevir), resulting in a sample size of 28 patients in each group. In a paired t-test analysis (from baseline to 12-month post-treatment), with $\alpha=0.05$, power of 90% ($1-\beta$), and standard deviation (σ) = 0.15, we will be able to detect a true difference in the mean hsCRP response of matched pairs of 0.1 mg/L in each group or 0.8 mg/L with 80% power.

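### Section 13.1 gives no basis for the SD of 0.15 mg/L behind its power claim, and that SD fits poorly with the mean and median cited in the same paragraph

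*Combined protocol and SAP*

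**What the plan says.** Section 13.1 takes 30 patients per treated group, assumes 95% reach SVR, "resulting in a sample size of 28 patients in each group", and powers a paired t-test at alpha 0.05 with "standard deviation (σ) = 0.15". For 90% power it concludes that "we will be able to detect a true difference in the mean hsCRP response of matched pairs of 0.1 mg/L in each group".

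The supporting data come from one cited study of interferon-treated HCV-monoinfected patients: "mean hsCRP before starting IFN-therapy in HCV-monoinfected patients was 0.97 ± 0.11 mg/L compared to 0.07 ± 0.07 mg/L in healthy controls". For responders it adds: "Among SVR patients the median hsCRP at baseline was 0.64 mg/L and decreased to 0.25 mg/L after treatment". The ± values are not labelled as SD or SE, and the size of the cited study and its SVR share are not given. No hsCRP data are given for co-infected patients.

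The hypothesis in 3.4 and 13.1 is at least a two-fold fall in hsCRP. Section 13.2 plans a paired t-test within each group and mentions no transformation.

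**The concern.** The power statement is the protocol's only sample-size justification, and it depends entirely on the SD of within-patient change. Nothing shows where 0.15 comes from. It is close to 0.11 × √2 = 0.156, the SD of a difference between two uncorrelated measurements with SD 0.11 each, so the cited ±0.11 may have been used as a patient-level SD. That origin is an inference.

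The same paragraph makes so small a spread hard to accept. The responders' median lies 0.33 mg/L below the cohort mean, which is three times 0.11. If the SD of change is really larger, the stated sensitivity is too favourable, and a null result could be read as excluding a change that the study could not reliably detect. The figure is also applied unchanged to Group 2, for which no data are offered.

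**Working it through.** **Inputs from 13.1.** n = 28 pairs; alpha 0.05 (two-sided assumed, as sidedness is not stated); SD 0.15 mg/L; cohort mean 0.97; ±0.11; SVR-patient median 0.64 falling to 0.25 mg/L.

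**1. The plan's own figure.** Exact paired-t power (noncentral t, 27 df) gives a standardised detectable effect of 0.636 SD at 90% power and 0.549 SD at 80%.
- 90%: 0.636 × 0.15 = 0.095 mg/L, which rounds to the stated 0.1. Power for exactly 0.1 mg/L is 92.5%.
- 80%: 0.549 × 0.15 = 0.082 mg/L. The printed "or 0.8 mg/L with 80% power" does not reproduce and looks like a decimal slip for 0.08. This is a separate error in the same sentence.

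**2. Is the SD compatible with the cited mean and median?** Take the SVR patients to be a subset of the cohort with mean 0.97, making up a share p of it. At least half of them, so at least p/2 of the cohort, lie at or below 0.64. The one-sided Chebyshev (Cantelli) inequality says that for any distribution at most 1/(1 + k²) lies k SDs or more below the mean.
- SD 0.11: k = 0.33/0.11 = 3.0; bound 1/(1 + 9) = 10%; so p ≤ 20%.
- SD 0.15: k = 0.33/0.15 = 2.2; bound 1/(1 + 4.84) = 17.1%; so p ≤ 34%.

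**3. Smallest baseline SD for a given p.** Rearranged: SD ≥ 0.33 × √[(p/2)/(1 − p/2)]. Assume equal SDs before and after treatment and a pre/post correlation r, so that SD of change = SD × √[2(1 − r)]. At r = 0.5 the two SDs are equal.

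| SVR share p | Minimum baseline SD (mg/L) | Detectable at 90% power, r = 0.5 (mg/L) | Power for 0.1 mg/L, r = 0.5 |
|---|---|---|---|
| 50% | 0.19 | 0.12 | 76% |
| 75% | 0.26 | 0.16 | 51% |
| 100% | 0.33 | 0.21 | 34% |

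**4. Sensitivity to the correlation.** At p = 50% and r = 0.7, SD of change = 0.1905 × √0.6 = 0.148 and power for 0.1 mg/L is 93%. At p = 100%, r must be about 0.90 to bring the SD of change down to 0.15.

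**5. The effect that matters.** The cited medians fall by 0.64 − 0.25 = 0.39 mg/L. Power stays at 90% or more while the SD of change is at most 0.39/0.636 = 0.61 mg/L. On the ln scale, power to show a fall when the true fall is two-fold is at least 90% if the SD of ln change is at most ln 2/0.636 = 0.693/0.636 = 1.09. For assumed ln SDs of 0.8, 1.0 and 1.2, the detectable falls are exp(0.636 × SD) = 1.66-, 1.89- and 2.14-fold.

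**The case against.** The strongest reply is that no contradiction has been proved. Cantelli bounds the baseline SD of the whole source cohort, whereas the paired t-test needs the SD of change in patients who reach SVR. The link runs through an SVR share and a correlation that the protocol does not give, and step 4 shows that a moderately high correlation can bring the floor back to 0.15. If ±0.11 is a genuine SD at both visits, the SD of change is at most 0.156 for any non-negative correlation, and power for 0.1 mg/L is still about 91%. All of this stands, and it limits the point to strong evidence. It does not validate 0.15: the floor is a minimum, reached only by an extreme two-point distribution, and the genuine-SD case requires SVR in at most 20% of the cohort.

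A reader might infer that the ± values are standard errors and that true sensitivity is therefore several times worse. The document does not support this. The controls are given as 0.07 ± 0.07. For non-negative values a standard error cannot exceed the mean, and equals it only if all but one value are zero, so a standard-error reading of that figure is near-impossible. Larger losses also need an assumed source sample size or an assumed lognormal shape. The lognormal fit would treat a mean from all patients and a median from responders as one distribution.

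It is also fair to say that 0.1 mg/L is not the hypothesised effect, that the study calls itself a pilot, and that nothing in the protocol says a null result would exclude 0.1 mg/L.

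**Conclusion.** The point holds as one about an unsupported input. The claimed 90% power for 0.1 mg/L follows from the SD of 0.15, but that SD has no stated source, is not identified as the SD of change, and is hard to reconcile with the cited mean and median unless SVR was uncommon in the source cohort. At the minimum baseline SD and correlation 0.5, the detectable difference is about 1.3 to 2.2 times the computed 0.095 mg/L (0.12 to 0.21). That range rests on the SVR share (50% to 100%), equal SDs at both visits and the correlation, none of which the protocol states.

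A reader might go further and conclude that the trial is underpowered for its primary hypothesis. The documents do not show that. A 0.39 mg/L fall keeps 90% power up to an SD of change of about 0.61 mg/L, well above the floor values. What is missing is a stated sensitivity tied to the two-fold hypothesis and to a justified SD. Severity: should-fix.

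**What to change.** In 13.1:
- Replace the SD of 0.15 and both mg/L claims (90% and 80% power) with the statement that 28 pairs at two-sided 0.05 detect 0.64 SD of within-patient change at 90% power and 0.55 SD at 80%.
- State power for the two-fold hypothesis on the ln scale: at least 90% if the SD of ln change is at most 1.09. Show ln SDs of 0.8, 1.0 and 1.2 (1.66-, 1.89- and 2.14-fold) as an assumed range, and cite paired data for the chosen value if any exist.
- Label the cited ± values as SD or SE.
- Say that no co-infected data support the figure for Group 2.

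In 13.2, specify the primary paired t-test on ln(hsCRP), so that the analysis matches both the fold-change hypothesis and the restated power.

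The cost is one rewritten paragraph and one amended sentence. Enrolment stays at 30 per group. The stated sensitivity becomes conditional on an assumed SD and less favourable than the present text.

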13.2 Statistical Analysis

We will perform univariate analysis to describe the demographic and clinical characteristics of the study population. Count with percentages will be calculated for categorical variables and mean + standard deviation or median (interquartile range) for continuous variables. The independent variable is the three groups of participants with HCV, HIV/HCV, and HIV. Separate analysis will be done for each study group for the change in the primary outcome of HsCRP, from baseline to 18 months after baseline, in a paired t-test analysis, as well as for the secondary outcomes of cardiac biomarkers, MRI, and cellular and soluble immune markers of activation. Baseline comparison of hsCRP, cardio biomarkers, MRI, and cellular and soluble immune markers of activation between the three groups of participants will be performed using one-way or Kruskal-Wallis analysis of variance (ANOVA) for continuous variables and chi-square test of independence or Fisher's exact test for categorical variables. A linear regression model will be used in adjusted analysis for continuous dependent variables, while logistic regression model will be used in adjusted analysis for binary dependent variables. All analysis will be conducted in SAS, version 9.4 (SAS Institute, Inc., Cary, NC) with a P-value of less than 0.05 indicating statistical significance.

14 Ethics/Protection of Human Subjects

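### Section 13.1 gives 0.8 mg/L as the hsCRP difference detectable at 80% power, larger than its own 0.1 mg/L at 90%; the stated inputs give about 0.08 mg/L.

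*Combined protocol and SAP*

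**What the plan says.** Section 13.1 (Sample Size Justification and Power) plans 30 patients per group and expects 95% of them to reach SVR, "resulting in a sample size of 28 patients in each group". The test is named next: "In a paired t-test analysis (from baseline to 12-month post-treatment"). Alpha is 0.05 and the standard deviation is 0.15. One sentence then gives two detectable mean differences under these inputs. The first, at 90% power, is 0.1 mg/L. The second follows directly: "matched pairs of 0.1 mg/L in each group or 0.8 mg/L with 80% power".

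No second sample size, standard deviation or alpha is given for the 80% figure, and no other section states a different one. Section 13.2 adds only the significance threshold, a "P-value of less than 0.05 indicating statistical significance". Neither section says whether the test is one- or two-sided, or whether 0.15 is the standard deviation of the within-patient differences or of hsCRP at a single visit.

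**The concern.** The two figures run in the wrong direction. For a given test, sample size, standard deviation and alpha, accepting lower power lets a study claim sensitivity to a smaller effect. Section 13.1 has the detectable difference rising eightfold, from 0.1 to 0.8 mg/L, as power falls from 90% to 80%.

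This is a power figure for the primary outcome, and a literal reading misleads. The same section cites a fall in median hsCRP among SVR patients from 0.64 to 0.25 mg/L, that is 0.64 − 0.25 = 0.39 mg/L. A detectable difference of 0.8 mg/L is about twice that fall and exceeds the cited baseline median itself. A reader would conclude that the study cannot detect its own expected effect at 80% power, which is the opposite of what the inputs imply.

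**Working it through.** **Inputs, all from section 13.1**

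- Pairs per group: n = 28 (30 × 0.95 = 28.5, taken as 28).
- Standard deviation: 0.15, read as that of the paired differences (assumption).
- Alpha: 0.05, read as two-sided (assumption).
- Test: paired t-test within each group, 27 degrees of freedom.

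**Method.** Power at a true mean difference d is the probability that a noncentral t variable with n − 1 degrees of freedom and noncentrality d√n / SD falls beyond ± the critical value, here t(0.975; 27) = 2.052. The detectable difference is the d at which this probability equals the target power. The normal approximation serves as a check: d ≈ SD × (z for alpha + z for power) / √n, with 0.15/√28 = 0.02835.

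**Step 1: the plan's 90% figure.** The exact value is 0.6356 × 0.15 = 0.0953 mg/L. The approximation is (1.960 + 1.282) × 0.02835 = 0.0919. Both round to the stated 0.1, and power at exactly 0.1 mg/L is 92.5%. This figure reproduces, which supports the reading of the inputs.

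**Step 2: the plan's 80% figure.** The exact value is 0.5492 × 0.15 = 0.0824 mg/L. The approximation is (1.960 + 0.842) × 0.02835 = 0.0794. The plan prints 0.8, and 0.8 / 0.0824 = 9.7. The ratio of the 80% to the 90% value is 0.0824 / 0.0953 = 0.864, against the printed ratio of 0.8 / 0.1 = 8.

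**Step 3: other readings, at 80% power.** Where 0.15 is taken as a per-visit standard deviation with correlation ρ between visits, the standard deviation of the differences is 0.15 × √(2(1 − ρ)).

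| Reading | Detectable difference (mg/L) |
|---|---|
| Two-sided, n = 28, SD of differences 0.15 | 0.082 |
| One-sided alpha 0.05 | 0.072 |
| n = 27 / 29 / 30 | 0.084 / 0.081 / 0.079 |
| Per-visit SD 0.15, ρ = 0 | 0.117 |
| Per-visit SD 0.15, ρ = 0.2 | 0.104 |
| Per-visit SD 0.15, ρ = 0.5 | 0.082 |
| Per-visit SD 0.15, ρ = 0.8 | 0.052 |

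None comes near 0.8. A two-sample formula with 28 per group gives 0.112 by the normal approximation, and pooling 56 pairs gives 0.057.

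**Step 4: what would make 0.8 right.** At n = 28 the standard deviation of the differences would have to be 0.8 / 0.5492 = 1.46 mg/L (two-sided) or 0.8 / 0.4821 = 1.66 mg/L (one-sided), about ten times the stated 0.15. With 1.46, the 90% figure would be 0.6356 × 1.457 = 0.93 mg/L, not 0.1. So no single standard deviation satisfies both halves of the sentence. With the stated 0.15, power at 0.8 mg/L is above 99.99%, and three pairs would already give 80%.

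**The case against.** The strongest reply is that this is a missing zero and nothing rests on it: the 30 per group is supported by the 90% statement, and section 13.2 makes no use of the 80% figure. That is correct, and it is why the point is an erratum and not a criticism of the study's size.

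A second reply is that the recomputed value depends on two things the plan leaves unstated. If 0.15 were a per-visit standard deviation, the correct 80% value could lie anywhere from 0.052 to 0.117 mg/L for the correlations tried. The 90% statement would then also be open to question: at ρ = 0 and ρ = 0.2 the 90% values become 0.135 and 0.121 mg/L, and power at 0.1 mg/L drops to 67% and 77%. This stands as a caution about the replacement number. It does not rescue 0.8, because the wrong direction of the two figures needs no assumption about sidedness or type of standard deviation. The standard deviation of the differences is also the natural input to a paired t-test, and it reproduces the plan's 90% figure on rounding.

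Two weaker replies remain. A study with near-certain power at 0.8 mg/L can literally detect 0.8 mg/L with at least 80% power, but the sentence plainly pairs two detectable differences with two power levels. A digit lost in reading the PDF cannot be strictly excluded, but the figures around it (0.07, 0.11, 0.15, 0.25) are intact and the text is continuous prose.

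**Conclusion.** The 80% figure in section 13.1 is wrong as written. That the two printed figures are incompatible holds without further assumptions. Its size, 0.8 against 0.082 mg/L, rests on a two-sided 0.05 test and on 0.15 being the standard deviation of the paired differences. A decimal slip for 0.08 is the likely cause, though that is an inference and the error does not depend on it. The 90% statement is not in dispute on the same reading. Severity is minor and confidence is high. Whether 0.15 is a realistic standard deviation for paired hsCRP differences is a separate question that was not examined here.

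**What to change.** In section 13.1, state that alpha is two-sided and that 0.15 is the standard deviation of the paired differences, if that is what is meant. On that basis, replace the 80% figure with about 0.082 mg/L and leave 0.1 mg/L at 90% as it is. If 0.08 is printed, mark it as rounded, because power at exactly 0.08 mg/L with 28 pairs is 77.7%. If 0.15 means something else, or is later revised, recompute both figures together.

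The cost is a one-line correction, with no change to sample size, analysis or conduct.

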13.2 Statistical Analysis

We will perform univariate analysis to describe the demographic and clinical characteristics of the study population. Count with percentages will be calculated for categorical variables and mean + standard deviation or median (interquartile range) for continuous variables. The independent variable is the three groups of participants with HCV, HIV/HCV, and HIV. Separate analysis will be done for each study group for the change in the primary outcome of HsCRP, from baseline to 18 months after baseline, in a paired t-test analysis, as well as for the secondary outcomes of cardiac biomarkers, MRI, and cellular and soluble immune markers of activation. Baseline comparison of hsCRP, cardio biomarkers, MRI, and cellular and soluble immune markers of activation between the three groups of participants will be performed using one-way or Kruskal-Wallis analysis of variance (ANOVA) for continuous variables and chi-square test of independence or Fisher's exact test for categorical variables. A linear regression model will be used in adjusted analysis for continuous dependent variables, while logistic regression model will be used in adjusted analysis for binary dependent variables. All analysis will be conducted in SAS, version 9.4 (SAS Institute, Inc., Cary, NC) with a P-value of less than 0.05 indicating statistical significance.

14 Ethics/Protection of Human Subjects

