2.2 Secondary Objectives

Determine the difference in change (pre vs. post functional cure) in cardiovascular risk among HCV monoinfected and HIV/HCV coinfecting patients compared to HIV monoinfected patients, using high-sensitivity C-reactive protein.

Compare the difference in levels of cardiac biomarkers between HCV monoinfected, HIV/HCV coinfecting, and HIV monoinfected patients at baseline

Determine the difference in change (pre vs. post functional cure) in cardiac biomarkers among HCV monoinfected and HIV/HCV coinfecting patients, compared to HIV monoinfected patients.

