2.3 Exploratory Objectives

1. Compare the difference in cardiac MRI between HCV monoinfected, HIV/HCV coinfecting, and HIV mono-infected subjects at baseline. MRI parameters that will be assessed are the native myocardial T1, myocardial T2, and myocardial extracellular volume fraction (to look for myocardial inflammation and small

vessel disease). Gadolinium enhancement will be used to look at macroscopic fibrosis.

2. Determine the difference in change (pre vs. post functional cure) in cardiac MRI in HCV monoinfected and HIV/HCV coinfected patients, compared to HIV monoinfected patients. MRI parameters that will be assessed are listed in exploratory objective 1.
3. Determine the relationship between immune markers of activation, cardiac biomarkers, and MRI in HIV positive and negative subjects. MRI parameters that will be assessed are listed in exploratory objective 1.
4. Compare the difference in levels of cellular and soluble immune markers of activation between HCV monoinfected, HIV/HCV coinfected, and HIV monoinfected subjects at baseline.
5. Determine the difference in change (pre vs. post functional cure) in cellular and soluble immune markers of activation HCV monoinfected and HIV/HCV coinfected patients, compared to HIV moninfected patients.

3 Study Design

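### The only explicit analysis of change in section 13.2 is a paired test within each group, although four objectives ask for the difference in change against HIV mono-infected patients

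*Combined protocol and SAP*

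**What the plan says.** Four objectives are worded as a difference in change, each relative to HIV mono-infected patients:

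- Secondary objective 1 (section 2.2), for hsCRP: "Determine the difference in change (pre vs. post functional cure) in cardiovascular risk among" the two HCV groups.
- Secondary objective 3 (section 2.2): "Determine the difference in change (pre vs. post functional cure) in cardiac biomarkers among" the same groups.
- Exploratory objective 2 (section 2.3): "Determine the difference in change (pre vs. post functional cure) in cardiac MRI in HCV monoinfected" and co-infected patients.
- Exploratory objective 5 (section 2.3): "Determine the difference in change (pre vs. post functional cure) in cellular and soluble immune markers of activation HCV monoinfected" and co-infected patients.

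Section 13.2 has four relevant statements:

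- On design: "The independent variable is the three groups of participants with HCV, HIV/HCV, and HIV".
- On change: "Separate analysis will be done for each study group for the change in the primary outcome of HsCRP", from baseline to 18 months, by paired t-test. The same sentence covers biomarkers, MRI and immune markers.
- On group comparisons: "Baseline comparison of hsCRP, cardio biomarkers, MRI, and cellular and soluble immune markers of activation between the three groups", by ANOVA or Kruskal-Wallis, with chi-square or Fisher's exact test for categorical variables.
- On modelling: "A linear regression model will be used in adjusted analysis for continuous dependent variables", with logistic regression for binary ones.

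Section 13.1 calls change in hsCRP the primary outcome and gives power only for the paired test within each group.

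**The concern.** A paired test in one group asks whether that group's mean change is zero. Three such tests, one per group, do not ask whether two groups changed by different amounts, and they give no interval for that difference. Yet this is what two of the three secondary objectives and two of the five exploratory objectives set out to learn, and it is the reason for following 30 controls to week 72.

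The objectives' wording also leaves open whether Groups 1 and 2 are each compared with Group 3 or are pooled, and 13.2 does not settle it. An analyst would have to choose the outcome, its scale, the contrast and the covariates after the data are in. The alternative would be to set the within-group p-values side by side, which can suggest a difference where none exists.

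**Working it through.** **1. Objectives against methods.** The two objective types that compare groups fare differently in 13.2. Baseline differences (secondary 2, exploratory 1 and 4) have named between-group tests. Differences in change (secondary 1 and 3, exploratory 2 and 5) have only the within-group paired test and the general regression sentence. That sentence does not name change as the dependent variable, Group 3 as the reference, or any covariate. Appendix B already schedules hsCRP, inflammation markers, T cells and MRI in HIV mono-infected patients before treatment and at week 72, so the data will exist.

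**2. The plan's own figure.** Inputs from 13.1: n = 28 per HCV group, SD 0.15 mg/L (taken as the SD of change), alpha 0.05 (two-sided assumed). By noncentral t, the paired test detects 0.095 mg/L at 90% power, which rounds to the stated 0.1. At 80% power it detects 0.082 mg/L; the stated 0.8 does not reproduce, which is a separate matter. No between-group figure is stated.

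**3. Precision of the missing contrast.** Assume the same SD of change, 0.15 mg/L, in Group 3 (n = 30, section 3.1), no loss to follow-up and no covariate adjustment.

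- Within one HCV group, 95% half-width = t(27) × SD/√n = 2.052 × 0.15/√28 = 0.058 mg/L.
- HCV group minus Group 3, half-width = t(56) × SD × √(1/28 + 1/30) = 2.003 × 0.15 × 0.2628 = 0.079 mg/L.
- Detectable difference at 80% power, 28 vs 30: 0.749 SD × 0.15 = 0.112 mg/L.
- MRI, at most 12 per group (section 6.2): 1.20 SD at 80% power, 12 vs 12.

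**4. Illustration: reading the separate tests across groups.** Let the true change be equal in an HCV group (28) and in Group 3 (30). The chance that the HCV test is significant and the HIV test is not equals power(28) × [1 − power(30)]:

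| True change (SD) | Power, n = 28 | Power, n = 30 | HCV significant, HIV not |
|---|---|---|---|
| 0 | 0.050 | 0.050 | 4.8% |
| 0.2 | 0.175 | 0.185 | 14% |
| 0.38 | 0.492 | 0.521 | 24% |
| 0.5 | 0.723 | 0.754 | 18% |
| 0.67 | 0.925 | 0.942 | 5.4% |
| 0.8 | 0.983 | 0.989 | 1.1% |

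A direct two-sided contrast rejects in 5% in every row. The row at 0.38 SD is close to the worst case. The row at 0.67 SD is the effect in 13.1 (0.1/0.15).

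**The case against.** The strongest reply is that the pieces are already there. Section 13.1 calls the primary outcome change in hsCRP, and 13.2 makes group the independent variable and names linear regression for continuous outcomes. Read together, regressing change on group is a natural reading, at least for secondary objective 1, and it would give group differences with intervals. This stands as far as it goes. A reader might infer that the plan rules out or cannot produce a between-group estimate, and the documents do not support that. But the regression sentence follows the baseline comparisons, can equally be read as adjusting those, and does not tie itself to change. Where 13.2 is explicit about change, it says the analysis is separate for each group.

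A second reply is that nothing in 13.2 says groups will be compared by which p-values fall below 0.05. That is correct. A reader might take the 24% as the plan's error rate. It is a chosen worst case of a misreading that the plan does not state, and nothing in the documents suggests that controls share a change of 0.38 SD with the treated groups.

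Third, this is a pilot whose primary objective is a within-group change. The paired test answers that objective, and leaving secondary contrasts unpowered is not an error. This also stands, so the precision figures above describe what the contrast can deliver and are not evidence of a power failure.

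**Conclusion.** The mismatch is real and should be fixed. Section 13.2's only explicit analysis of change is within each group, its named between-group tests are for baseline, and four objectives need a contrast of change with Group 3 that no sentence states. The primary objective, its test and its power statement are untouched.

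The conclusion rests on the text and needs no assumption about variance. The sizes attached to it do. The half-widths and the mg/L detectable difference assume an SD of change of 0.15 mg/L in both groups, 28 and 30 patients with complete data, and no adjustment. The MRI figure assumes that all 12 places per group are filled and that both scans are obtained. The false-pattern rate, about 5% to 24% for equal true changes between 0 and 0.67 SD and lower above that, applies only if someone compares the separate p-values.

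**What to change.** Keep the paired analysis for the primary objective. Add to 13.2, for secondary objectives 1 and 3 and exploratory objectives 2 and 5:

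- **Model:** change from baseline to week 72 (the 18 months already in 13.2) is regressed on group with the baseline value as a covariate. For hsCRP the log scale is used, to match the two-fold hypothesis in section 3.4.
- **Contrasts:** Group 1 minus Group 3 and Group 2 minus Group 3, each with a 95% confidence interval. Separate contrasts match 13.1, which states the hypothesis for each HCV group in turn.
- **Patients:** the same HCV patients as in the within-group analysis (13.1 counts those with SVR, 28 per group).
- **Claims:** any statement relative to controls rests on these contrasts, not on comparing within-group p-values. They are labelled secondary or exploratory, without multiplicity control.

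The cost is a few sentences and a little programming, with no new visits, samples or patients. The contrast is less precise than the within-group result, markedly so for MRI. Repeating it over many markers will produce some chance findings, hence the labelling. Adjustment for baseline does not remove confounding, because the groups are not randomised, and the report should say so.

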2.1 Primary Objective

Determine the change in cardiovascular risk from baseline to after functional cure of hepatitis C among HCV monoinfected and HIV/HCV-coinfected patients, using high-sensitivity C-reactive protein.

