3.1 Description of the Study Design

This is a pilot, intervention, non-randomized, controlled prospective study. We will enroll 90 patients into the following groups. Up to 200 patients will be consented.

Group 1: HCV mono-infected patients (n = 30)

Group 2: HIV/HCV co-infected patients (n = 30)

Group 3: HIV mono-infected patients (n = 30)

Patients with HCV mono-infection (Group 1) or HIV/HCV co-infection (Group 2) will receive therapy with any FDA-approved medication for hepatitis C treatment, per standard of care in the AASLD/IDSA HCV Treatment Guidelines and/or the discretion of the investigator.

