3.4 Primary Hypothesis

The primary hypothesis is that treatment and functional cure of HCV in HCV-monoinfected and HIV/HCV-coinfected patients should lead to decreased cardiovascular risk, as measured by at least a 2-fold decrease in high-sensitivity C-reactive protein (hsCRP) by 12 months post-functional cure of HCV.

4 Study Population

Participants are adults (age 18-70) patients infected with HIV, HCV and HIV/HCV.

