6.4.3 Viral sequencing

Individuals with new seroconversion to HIV will have sample sent for viral sequencing and phylogenetic analysis. Individuals with detectable HCV RNA after completion of HCV treatment or new infection during the follow up period will have current sample, and baseline stored sample sent for viral sequencing and phylogenetic analysis.

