6.5 Early Termination Visit

Participants who discontinue HCV treatment prior to treatment completion for medical or personal reasons will be given the option of being followed as per study schedule for lab monitoring.

7 Potential Risks and Benefits

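### Does the wording of section 13.2 put uncured participants into the primary hsCRP analysis?

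*Combined protocol and SAP*

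**What the plan says.** The primary objective (2.1) reads "Determine the change in cardiovascular risk from baseline to after functional cure of hepatitis C among HCV monoinfected and HIV/HCV-coinfected patients", measured by hsCRP. The primary hypothesis (3.4) is "at least a 2-fold decrease in high-sensitivity C-reactive protein (hsCRP) by 12 months post-functional cure of HCV". Section 13.1 sizes the study on cured participants: "we assume than 95% will achieve SVR with Zepatier (elbasvir/grazoprevir), resulting in a sample size of 28 patients in each group". It takes its effect from the same kind of patient: "Among SVR patients the median hsCRP at baseline was 0.64 mg/L and decreased to 0.25 mg/L after treatment".

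Section 13.2, the only analysis section, says "Separate analysis will be done for each study group for the change in the primary outcome of HsCRP", using a paired t-test. The groups there are HCV, HIV/HCV and HIV, that is, infection status. It does not mention cure, an analysis population, or how non-responders or reinfected participants are treated.

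Functional cure is equated with SVR in 1.1 and again in exclusion criterion 7 of 4.3. Section 6.4.2 leaves HCV RNA testing to standard of care. Appendix B marks it for the HCV groups at screening, end of treatment, week 24 and week 72.

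**The concern.** The question is about cured people, but the analysis sentence is about groups of 30 defined before treatment. The plan expects some participants not to be cured and makes it possible for them to have a week 72 hsCRP. Section 6.4 schedules the draw for everyone. Section 6.5 says that those who stop HCV treatment early "will be given the option of being followed as per study schedule for lab monitoring". Section 6.4.3 anticipates "Individuals with detectable HCV RNA after completion of HCV treatment or new infection during the follow up period".

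If those participants are analysed, an estimate labelled as the change after cure would mix cured and viraemic people and be pulled towards no change. If they are left out, someone has to decide which HCV RNA result counts. A participant who is undetectable at week 24 and detectable at week 72 could be classed either way. The worry is that this choice might be made with the data in view, and that the 2-fold hypothesis might hold in one set and fail in the other.

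**Working it through.** **The plan's own figures (13.1).** 30 × 0.95 = 28.5, stated as 28. For a paired t-test with n = 28, SD of the differences 0.15 and two-sided alpha 0.05 (sidedness is not stated; two-sided assumed), the detectable difference at 90% power is 0.095 mg/L, which agrees with the stated 0.1. With n = 30 it is 0.092. The choice of set hardly alters it.

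**Power at a true change of 0.1 mg/L in the cured.**
- Cured only, n = 28: 92.5%.
- All 30 with 2 uncured and unchanged: mean change (28/30) × 0.1 = 0.093; SD √(0.15² + (28/30)(2/30) × 0.1²) = 0.152; power 90.1%.

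Both meet the planned 90%.

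**Size of the decrease.** Assumptions: the medians in 13.1 are used as means, baseline is fixed at 0.64, participants viraemic at week 72 do not change, and the SD of change is 0.15.
- Cured set: 0.64/0.25 = 2.56-fold.
- All 30 with k viraemic: week 72 mean = ((30 − k) × 0.25 + k × 0.64)/30.
- A 2-fold decrease means a week 72 mean of 0.32 or less. The chance of observing that is Φ((0.32 − mean)/(0.15/√n)).

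| Set | Week 72 mean | Fold decrease | Chance observed mean reaches 2-fold |
|---|---|---|---|
| Cured, n = 28 | 0.250 | 2.56 | 0.99 |
| n = 30, k = 2 | 0.276 | 2.32 | 0.95 |
| n = 30, k = 4 | 0.302 | 2.12 | 0.74 |
| n = 30, k = 6 | 0.328 | 1.95 | 0.39 |

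In simulation of the three n = 30 rows (100,000 runs) the paired t-test gave p<0.05 in every run.

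**Scale.** Fold change is naturally read as a ratio. On the geometric scale the decrease is 2.56^((30 − k)/30): k = 2 gives 2.40-fold and k = 6 gives 2.12-fold. The shortfall at k = 6 is therefore specific to the arithmetic scale.

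**Which k the plan supports.** The plan's own split is 28 cured of 30, so k = 2. Under a binomial with 95% SVR, the probability of 26 or more cured is 0.984, so 5 or more non-responders in a group has probability 0.016. At k = 5 the mean is 0.315, still 2.03-fold. Reaching k = 6 would require a much lower cure rate or substantial reinfection, and the documents give no reinfection rate.

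**Where the two sets would disagree.** The set of 30 reaches 2-fold when the cured-set decrease F is at least (30 − k)/(15 − k). For k = 2 that is 28/13 = 2.15. A cured-set decrease from 2.00-fold up to 2.15-fold would pass in one set and fail in the other. The plan's 2.56 lies outside that band.

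**Reading 13.1 with 13.2.** Section 13.1 specifies a paired t-test of the primary outcome on the SVR patients in each group. Section 13.2 names the same test and outcome by group and says neither all nor whole. Sections 6.4 and 6.5 govern blood collection, not inclusion in the analysis.

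**The case for a change.** The strongest case for a change is that 13.1 gives only a count for power, while 13.2 is the section that governs analysis and does not carry the restriction over. An analyst who wants the 28 cannot identify them from the documents, because no HCV RNA result is named. The study has a numerical hypothesis and a powered test, so being a pilot does not excuse the omission. A few sentences, using RNA results already scheduled, would settle it.

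It stands that the analysis set and the SVR criterion are unwritten, and that a true decrease close to 2-fold could be read differently in the two sets.

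The rest is weaker. The plan cannot both require viraemic participants in the analysis and leave the set open; only the second is supported by the text. Section 13.2 contains no test of the 2-fold criterion, so no decision rule depends on the choice of set. Nor is restricting to the cured plainly better. Cure is a post-baseline outcome, and an all-treated analysis is defensible and, if the uncured do not change, conservative.

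Writing a rule would not by itself remove the mixing. If cure is classified at week 24 and those later viraemic stay in the set, four such participants among 28 give (24 × 0.25 + 4 × 0.64)/28 = 0.306, or 2.09-fold, much the same dilution. Section 6.4.3 also sends the current and baseline samples of anyone viraemic after treatment for sequencing, which helps an analyst separate relapse from new infection.

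**Conclusion.** This is missing detail that an analyst would fill sensibly from 2.1, 3.4 and 13.1, by analysing the SVR participants with both draws and showing all treated participants beside them. Choosing between those two sets is a fair trade-off, and the plan does not commit itself to the less suitable one. At the plan's own figures even the most literal reading moves the expected decrease from 2.56-fold to 2.32-fold (2.40-fold geometric), leaves the 2-fold hypothesis met with chance 0.95 instead of 0.99, and leaves the significance test unaffected. These figures rest on no change in viraemic participants, medians standing in for means, an SD of change of 0.15, and 2 of 30 uncured. If viraemia at week 72 were several times more common than the plan assumes, the gap would matter more, but nothing in the documents points to that. No change to the plan follows.
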